## Randomization

Immediately following phase 1 testing on day 14, participants will be randomized to one of two experimental groups, either a 28-d (live-in), 55% energy deficit phase (DEF) or a 28-d (live-in), 55% energy deficit phase with exogenous testosterone administration (DEF+TEST). A randomization scheme will be determined using a block design (n=60) and age stratification (< 29 years or ≥ 29 years). Randomization will be done by a biostatistician with no direct study affiliation. Prior to the start of the study, the randomization schedule will be given to the pharmacist. The PBRC clinical research pharmacist will have no direct contact with participants. Treatment administration will be performed by a physician assistant, nurse practitioner, or nurse who will not be aware of treatment assignments. Participants and all study personnel will be blinded to treatment group. The code will be kept as a locked electronic file on a secure server by the pharmacist until study completion or there is a need to break the code for safety of the participant.

## Phase 2: 55% Energy Deficit (live-in diet & activity control). Day 15–Day 42

- During the energy deficit phase, participants will live on Pennington Biomedical's inpatient unit in a 24-hour-a-day controlled setting. Once a day, participants will have their vitals (BP, pulse) measured. All meals will be eaten on the unit and monitored. Daily, participants will be weighed. Additionally, a wrist-worn accelerometer will be used throughout phase 2.
- Throughout phase 2, participants will complete supervised exercise sessions 1-4 times per day. Every 2 weeks, participants will undergo submax met carts for each mode of exercise utilized.
- Participants will consume 100 mL/d  $^2\text{H}_2\text{O}$  (i.e., heavy water) from day 15 to 42.
- Participants will be asked to provide a saliva sample on days 15, 19, 23, 27, 31, 35, and 39 to assess body water enrichment.
- Blood draws will occur on days 28 and 42.
- Cognitive testing will be performed on days 15, 20, 22, 27, 29, 34, 36, 40 and 41 over a 1.5-2 hour period each day.
- A DXA scan will be done on days 28 and 39.
- A 1 hour fMRI will be done on days 36, 37, and 38.
- An injection (placebo or testosterone) will be administered on days 15, 21, 28, and 35.
- Eating Inventories (TFEQ, FCI, FCI trait) will be completed on day 42.

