### Questionnaires, MMPI-2, RTMITE Test, Risk-Assessment, and Cognitive/Vigilance Tests

**Training:** All volunteers will undergo training and familiarization with all behavioral tests (with the exception of the MMPI-2, on which there is no "training curve"). Introductory training and familiarization on the subjective scales, RTMITE test, the risk-assessment task and Ultimatum Game, and the cognitive/vigilance assessments will occur at 6 different points during the 14-day lead-in phase of the study. The entire battery of tests (questionnaires, RTMITE, and computerized cognitive and risk tests) will be administered upon arrival at the test facility on Day 0. Subsequently, on days 2, 4, 6, 8, and 10, following the packing of take-home meals and snacks, there will be an additional test-training session (one per day) which will include all of the previously-mentioned tests with the exception of select questionnaires (i.e., those on which there is no "training curve").

**Baseline Testing:** On Day 13, volunteers will complete a final lead-in, pre-intervention test battery which will consist of the entire suite of tests to include the questionnaires. Data from this test session which will serve as the baseline data (i.e., before the energy deficit/testosterone phase). Providing subjects with 6 pre-baseline test-training sessions along with 1 baseline questionnaire-familiarization session should be more than sufficient to minimize the influence of training effects on all of these instruments,

and therefore should ensure valid baseline results from the Day-13, pre-energy-deficit/testosterone-intervention phase of the protocol.

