**28-d Energy deficit testing:** Once the live-in, intervention portion of the protocol begins, volunteers will be asked to complete all of the subjective questionnaires (excluding the MMPI—see below), and risk/cognitive tests at 8 different points prior to the time at which they will return to free living. These cognitive test sessions will occur on Days 15, 20, 22, 27, 29, 34, 36, and 41. Note that 3 pairs of these sessions (D20 and D22, D27 and D29, and D34 and D36) are positioned so that they immediately surround the second, third, and fourth testosterone (or placebo) administrations on days 21, 28, and 35 in order to facilitate the examination of acute pre/post dose effects. Session on D15 occurs on the same day as the first injection. A determination regarding which sets of sessions will most appropriately describe the overall cumulative impact of the testosterone/calorie-deprivation intervention will depend on whether or not a preliminary analysis indicates the presence of significant differences between the 3 pairs of pre/post testosterone-administration sessions. Regardless of the outcome of this analysis, the session on Day 41 which is 1 day prior to the end of the entire intervention cycle (and 6 days after the final testosterone dose administration) will provide a valid end-point assessment of any cumulative calorie-deprivation/testosterone effects. With regard to the MMPI-2, it will be administered only on a single pre-intervention day (Day 5) and a single near-end-of-intervention day (Day 40) to explore the impact of caloric restriction and testosterone supplementation on several of the more stable aspects of personality.

**Recovery/Ad-libitum feeding testing:** During the final portion of the protocol, volunteers will be asked to complete two final questionnaire/test assessment sessions. The first will be on Day 54, and the second will occur at EOS.

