## Objective II: Statistics

Individualized scale scores from each of the questionnaires, the MMPI-2, and the RTMITE, the scores from the Ultimatum Game, the number of points earned on the Balloon Task, and dependent measures (such as accuracy scores and reaction times) on the vigilance, memory, and reasoning tasks will be analyzed with a series of mixed-factorial ANOVAs. Significant main effects and interactions will be pursued with Analysis of Simple Effects followed by appropriate linear contrasts and pairwise comparisons.

On all assessments there will be 2 levels of the grouping factor: Intervention (Energy Deficit-Androgen Maintenance and Energy Deficit+Androgen Maintenance). For preliminary examination of immediate pre/post-dose effects (on tests other than MMPI), the primary analysis will include the single grouping factor of Intervention with two within-subjects factors: Dose-iteration (Dose2, Dose3, Dose4) and Pre-post (Pre-dose, Post-dose). For examination of cumulative treatment effects (on tests other than MMPI), the primary analyses will include the Intervention grouping factor (Energy

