Deficit-Androgen Maintenance and Energy Deficit+Androgen Maintenance) and a single within-subjects factor labeled Session, minimally with 7 levels (Baseline, Intervention1, Intervention2, Intervention3, Intervention4, Recovery1, and Recovery2). The specific sessions chosen for this “cumulative-treatment-effect” analysis will depend on whether or not acute testosterone dose effects are found in the previously-described separate examination of immediate pre/post dose effects (described above). If acute post-dose effects appear to have occurred, the Sessions will consist of: Baseline-Day13, Live-In-Day21, Live-In-Day27, Live-In-Day34, Live-In-Day41, AdLib-Day54, and AdLib-Day83. In this case, note that all of the Live-In sessions are 6 days removed from (i.e., following) the testosterone dose administrations. If the preliminary analysis indicates no differences between the immediate pre/post dose administrations, an analysis may be performed on all of the data-collection sessions, or possibly only on the Live-In sessions that immediately follow each of the testosterone dose administrations (i.e., Baseline-Day13, Live-In-Day15, Live-In-Day22, Live-In-Day29, Live-In-Day36, AdLib-Day54, and AdLib-Day83. In this latter case, note that all of the Live-In sessions occur on the very next day after testosterone has been injected. With regard to the MMPI-2, since it is only to be administered twice, there will be 2 levels of the Intervention grouping factor and 2 levels of the Session within-subjects factor (Baseline, and End-Of-Intervention Day 40).

ReadiBand activity/sleep-monitoring data (sleep duration, sleep latency, and sleep efficiency) will be analyzed via a mixed factorial ANOVA for Intervention (Energy Deficit-Androgen Maintenance and Energy Deficit+Androgen Maintenance) by Period (Baseline, Live-In1, Live-In2, Live-In3, Live-In4, Live-In5, Ad-lib). In addition, average sleep data during the acclimation (free-living) phase will be more generally compared to average sleep data during the intervention and ad-libitum (free-living) phases with a 2x3 ANOVA. Significant interactions from both sets of analyses will be followed up with Analysis of Simple effects and appropriate post-hoc comparisons. Depending on the pattern of observed effects, a more fine-grained analysis (which would potentially include every night of ReadiBand data) may be conducted as well.

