#### Physiological outcomes

Mixed-model repeated measures ANOVA will be used to test the effects of testosterone maintenance on changes in appetite, postprandial endocrine responses, intestinal permeability, and SCFA concentrations over time. Postprandial appetite ratings and responses of endocrine mediators of appetite will be summarized using area under the

curve and peak/nadir concentration prior to analysis. Mixed-models will include subject as a random factor, study day and group as fixed factors, and the day-by-group interaction. Akaike's information criterion will be used to determine appropriate covariance structures. When a statistically significant time-by-group interaction is detected ( $P < 0.05$ ), all possible within- and between-group comparisons will be completed, and the familywise error rate adjusted using the Bonferroni correction.

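### Objective II uses the pre-randomization score only as a Session level, which dilutes the Intervention main effect and leaves baseline differences between men in the between-arm comparisons

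*Combined protocol and SAP*

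**What the plan says.** Under Objective II: Statistics, scores are analysed by mixed-factorial ANOVA with two Intervention groups and "a single within-subjects factor labeled Session, minimally with 7 levels (Baseline, Intervention1, Intervention2, Intervention3, Intervention4, Recovery1, and Recovery2". For MMPI-2 the design is two by two, with "2 levels of the Session within-subjects factor (Baseline, and End-Of-Intervention Day 40". The follow-up rule covers both kinds of effect: "Significant main effects and interactions will be pursued with Analysis of Simple Effects followed by appropriate linear contrasts and pairwise comparisons". No covariate is named anywhere in that section.

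The Baseline Testing paragraph says of Day 13: "Data from this test session which will serve as the baseline data (i.e., before the energy deficit/testosterone phase". The Randomization section assigns arms on day 14, and under Phase 2 "An injection (placebo or testosterone) will be administered on days 15, 21, 28, and 35". MMPI-2 is given on days 5 and 40. Of the two recovery sessions, "The first will be on Day 54, and the second will occur at EOS". Two alternative sets of live-in sessions are listed, and a preliminary analysis of acute dose effects chooses between them. One set starts at Day 21, the other at Day 15.

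The Objective III A-B statistics also enter study day as a fixed factor with no covariate. There, follow-up depends on a significant time-by-group interaction, after which "all possible within- and between-group comparisons will be completed, and the familywise error rate adjusted using the Bonferroni correction".

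**The concern.** Hypothesis II-C asks whether testosterone attenuates fatigue and protects mental performance during the deficit. The plan offers three routes to an answer and does not say which one decides.

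- **Intervention main effect.** It averages the arm difference over all sessions. Baseline contributes zero by design.
- **Between-arm simple effects at one session.** These compare raw arm means. They ignore what each man scored on Day 13, although six training sessions were scheduled to make that score reliable.
- **Intervention by Session interaction.** It compares sessions within men, so it uses baseline implicitly. But it asks on 6 degrees of freedom whether the arm difference varies over sessions, not whether the arms differ while on treatment.

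At stake is precision on a named hypothesis with about 25 men per arm. Randomization is stratified on age only, so a chance baseline imbalance would pass uncorrected into the first two routes.

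**Working it through.** **Inputs from the documents.** 25 completers per arm (Table 2); baseline Day 13, injections from day 15, recovery sessions Day 54 and EOS; two-sided 0.05 (stated for Objectives I and III; Objective II states no level).

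**Assumptions, because the documents give no effect size or correlation for Objective II.** SD 1 at each session, the same correlation r between any two sessions, live-in difference d = 0.5 SD (0.6 SD for MMPI-2).

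**The plan's own figure.** The only sample-size calculation concerns lean body mass: difference 3.0 − 2.25 = 0.75 with SD 0.75, effect size 1.0. Then n = 2(1.960 + 1.282)² = 21.0, rounded up to 22 per group, and t-test power at 22 is 0.90. It reproduces. There is none for Objective II.

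**1. Dilution of the main effect.** It estimates the mean of seven session differences.
- No effect at recovery: 4d/7 = 0.57d.
- Half persists: (4d + 2 × 0.5d)/7 = 5d/7 = 0.71d.
- Full persistence: 6d/7 = 0.86d.

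**2. Error variance per man.** The seven-session mean has variance (1 + 6r)/7 = 0.571, 0.743, 0.829 at r = 0.5, 0.7, 0.8. The stable between-man part is r, which is 88%, 94% and 97% of it. The four-session live-in mean has (1 + 3r)/4 = 0.625, 0.775, 0.850. Adjusting for baseline subtracts r², leaving 0.375, 0.285, 0.210.

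**3. Power, d = 0.5 in all four live-in sessions.** For the t-tests, noncentrality = estimate/√(2V/25). Main effect at r = 0.5: (4/7 × 0.5)/√(2 × 0.571/25) = 1.34, power 0.26. For the interaction, λ = (25/2) × Σ(δ − mean δ)²/(1 − r) on 6 and 288 df. At r = 0.5 with no effect at recovery, λ = 12.5 × 0.4286/0.5 = 10.7, power 0.67.

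| Effect at recovery | r | Main effect | Interaction | Live-in mean, baseline-adjusted |
|---|---|---|---|---|
| none | 0.5 | 0.26 | 0.67 | 0.81 |
| none | 0.7 | 0.21 | 0.90 | 0.90 |
| none | 0.8 | 0.19 | 0.98 | 0.97 |
| half | 0.5 | 0.37 | 0.38 | 0.81 |
| full | 0.5 | 0.50 | 0.35 | 0.81 |
| full | 0.7 | 0.41 | 0.57 | 0.90 |

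**4. One session, between arms, d = 0.5.** Unadjusted variance is 1: noncentrality 0.5/√(2/25) = 1.77, power 0.41 at any r. Adjusted variance is 1 − r²: power 0.52, 0.68, 0.82 at r = 0.5, 0.7, 0.8.

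**5. MMPI-2, d = 0.6.** The two-by-two interaction tests the change score, variance 2(1 − r). Adjusted variance is 1 − r². At r = 0.5 these are 1.00 and 0.75: noncentrality 2.12 and 2.45, power 0.55 and 0.67. At r = 0.3, 0.7, 0.8 the pairs are 0.42 and 0.59, 0.77 and 0.83, 0.91 and 0.93.

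**6. Type I error.** In 3,000 simulated trials under no effect (r = 0.7), rejection rates were 0.047 (main effect), 0.051 (interaction) and 0.051 (adjusted live-in mean).

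**The case against.** The strongest reply is that the planned interaction already removes stable differences between men. A reader might infer that the analysis ignores baseline altogether. It does not. The error-term point applies to the main effect and to between-arm simple effects, not to the interaction or to simple effects of Session within an arm. The plan also allows linear contrasts, so a live-in-versus-baseline contrast would fit within it.

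A reader might also infer that a baseline-adjusted live-in mean is always the stronger test. The flat pattern in the table favours it. With no effect at recovery, other patterns do not:

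| Live-in differences (SD) | r | Interaction | Adjusted live-in mean |
|---|---|---|---|
| 0, 0.5, 0.5, 0.5 | 0.5 | 0.67 | 0.56 |
| 0, 0.25, 0.5, 0.75 | 0.5 | 0.80 | 0.56 |
| 0.125, 0.375, 0.625, 0.875 | 0.5 | 0.91 | 0.81 |

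These patterns are also assumptions, but plausible ones. One listed session set includes Day 15, the day of the first injection, and the analysis is meant to capture cumulative effects. So a single averaged contrast is a trade-off. What survives is that the interaction loses power when the effect persists into recovery.

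Dropping Baseline from the model would also have a price. Objective II-A and the first appetite hypothesis of Objective III-A concern what the deficit itself does. With no arm free of the deficit, they need baseline as a time level.

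Finally, the recovery sessions are off drug but may carry an effect. Only Baseline is certainly untreated, hence a range for the dilution. In Objective III only the interaction triggers follow-up, so the diluted-main-effect point does not carry over there.

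**Conclusion.** The point stands as a loss of precision and a diluted main effect. With the session set that starts at Day 21, the Intervention main effect estimates 4/7 to 6/7 of the live-in difference. With the set that starts at Day 15 it could be as low as 3/7, if that session and recovery carry no effect. Single-session comparisons and MMPI-2 gain from adjustment at every correlation tried, less for MMPI-2 as the correlation rises (0.91 to 0.93 at 0.8).

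A reader might infer bias or false positives from baseline sitting among the outcomes. The documents do not support that: baseline precedes randomization, so neither arm is favoured in expectation, and the null rejection rates are near 0.05. The dilution follows from the listed sessions. Every power figure rests on assumed effect sizes, correlations and equal correlation between sessions. The change is worth making because the scores are already scheduled.

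**What to change.** - **Keep** the Intervention by Session model with Baseline as a level, for the within-arm deficit questions (Objective II-A) and as the omnibus test.
- **For Hypothesis II-C**, state that the Intervention main effect that includes Baseline will not be interpreted. Estimate between-arm differences at the live-in sessions from a model of the post-randomization sessions with the Day 13 score as covariate. A model that keeps Day 13 as an outcome but constrains the arm means there to be equal does the same job. Make recovery a separate contrast. State in advance whether the live-in differences are reported by session or averaged, given the trade-off above.
- **For MMPI-2**, regress the Day 40 score on arm and the day 5 score.
- **For Objective III**, adjust the between-arm comparisons at end of deficit and EOS for the pre-deficit value: day 7 for appetite, day 11 for permeability and short-chain fatty acids, day 14 for the eating inventories. Keep the time factor for the change-from-baseline hypotheses.

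The cost is one degree of freedom and one additional model per score. No new data are needed.

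### Objective II Statistics names cognitive sessions and fMRI periods that the schedule does not collect, and leaves one choice of sessions open when the preliminary test is negative

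*Combined protocol and SAP*

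**What the plan says.** Objective II: Statistics first tests for acute effects around doses 2 to 4, using Intervention, Dose-iteration and Pre-post. The result decides which sessions enter the cumulative-effect analysis, whose Session factor is to have at least seven levels.

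- **Set A, if acute effects are found:** "If acute post-dose effects appear to have occurred, the Sessions will consist of: Baseline-Day13, Live-In-Day21, Live-In-Day27", followed by Days 34, 41, 54 and 83. The plan adds: "note that all of the Live-In sessions are 6 days removed from (i.e., following) the testosterone dose administrations".
- **If none are found:** either every data-collection session, or possibly only **set B**, which is Days 13, 15, 22, 29, 36, 54 and 83. Of set B the plan says: "note that all of the Live-In sessions occur on the very next day after testosterone has been injected".

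The schedule appears elsewhere. The Phase 2 section of the Study Timeline says "Cognitive testing will be performed on days 15, 20, 22, 27, 29, 34, 36, 40 and 41" and "An injection (placebo or testosterone) will be administered on days 15, 21, 28, and 35". The cognitive-testing methods, under 28-d Energy deficit testing, say "These cognitive test sessions will occur on Days 15, 20, 22, 27, 29, 34, 36, and 41" and "Session on D15 occurs on the same day as the first injection". Day 40, the one extra day in the first list, is the MMPI-2 day. The methods put the last assessment at EOS. They also treat Day 41 as a valid end-point whatever the preliminary test shows ("Regardless of the outcome of this analysis, the session on Day 41").

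For fMRI, Objective II: Statistics crosses Intervention with seven periods: baseline, five live-in and one ad-lib. Functional MRI assessments has each task performed once in each of the three phases.

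**The concern.** Two of the stated models ask for data that the schedule does not produce: set A needs a Day 21 session, and the fMRI model needs five live-in levels. Set B can be run, but its description of time since dose is wrong for one of its four live-in sessions. An analyst would have to improvise.

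Where the preliminary test is negative, the plan does not say which of two analyses is the analysis. If that is settled after group-coded results are visible, the nominal error rate no longer holds. The rule covers nearly the whole cognition and mood battery, so the choice recurs for each outcome.

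**Working it through.** **Session days against injection days.** Injections are on Days 15, 21, 28 and 35. Scheduled live-in cognitive sessions are Days 15, 20, 22, 27, 29, 34, 36 and 41. Lag = session day minus the matching injection day.

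| Set | Live-in days | Lags (days) | Stated | All scheduled? |
|---|---|---|---|---|
| A as listed | 21, 27, 34, 41 | 21-15=6, 27-21=6, 34-28=6, 41-35=6 | 6 | No: Day 21 is missing |
| A with Day 20 | 20, 27, 34, 41 | 20-15=5, then 6, 6, 6 | 6 | Yes |
| B | 15, 22, 29, 36 | 15-15=0, 22-21=1, 29-28=1, 36-35=1 | 1 | Yes |

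The six-day lags are reproduced for the days that set A lists, but one of those days has no session. Dropping Day 21 leaves 7-1=6 levels, below the plan's own minimum of seven. Using Day 20 restores seven levels, with a first lag of 5 days.

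**Day 83.** Phase 3 lasts at most 42 days, so EOS can fall as late as Day 42+42=84, and earlier for anyone who regains body mass sooner. Day 83 is day 83-42=41 of phase 3. It is neither the maximum nor a scheduled visit.

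**fMRI.** Scan days are 5/36/55 for tasks 1-2, 9/37/56 for tasks 3-4 and 12/38/57 for tasks 5-6. Each task therefore has three scans, one of them live-in. The model has 2 x 7 = 14 cells and the data fill 2 x 3 = 6. Four of the five live-in levels are empty for every task. Even pooled over tasks, live-in scans fall on only three days. The allowed rescheduling moves phase 1 scans and task pairings but adds no scan.

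**The open choice.** The plan gives no error rate to reproduce, so this part is a simulation with no drug effect. Assumptions: 25 completers per arm, as in the sample-size section; 11 sessions (1 baseline + 8 live-in + 2 recovery); normal data; compound-symmetric correlation of 0.3, 0.5 or 0.8; two-sided 0.05, borrowed from Objective I because Objective II states no level; Day 20 in place of Day 21 in set A; and Intervention x Pre-post as the deciding term. The outcome is the Intervention x Session F-test.

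- Any one set, fixed in advance: about 5%.
- Preliminary rule followed, with the negative branch fixed to one option (all sessions or set B): about 4.4-5.3%.
- Preliminary rule followed, with whichever of the two options is significant reported: about 6.7-7.1%.

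For a t-test on mean live-in change from Day 13, the last figure is 6.4-6.6%. Without the preliminary test, the same t-test gives 6.5-6.6% if either option may be reported, or 5.9% if correlation is assumed to fade over days.

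**The case against.** Several points on the other side are sound.

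- **Set A's lag.** A reader might infer that the six-day statement is itself a miscalculation. It is not: 21-15=6. The 5-day lag arises only once the scheduled Day 20 session is substituted. The defect is the missing session.
- **The preliminary test.** A reader might infer that letting a first look at the data pick the sessions inflates the error rate. In the settings simulated it does not. The excess comes only from the unresolved choice after a negative test, and only if the significant option is the one reported, which the plan does not say will happen.
- **The deciding term.** The preliminary model contains Intervention and the text speaks of acute testosterone effects, so Intervention x Pre-post is the natural reading. The methods section and the negative branch mention only pre/post differences, so naming the term is a clarification.
- **Day 41.** Its absence from set B is not a contradiction. The methods call it a valid end-point but do not require it in every session set.
- **The design's logic.** Using sessions at a constant distance from dosing when acute effects exist is reasonable. Dropping the conditional rule altogether would be partly a preference.
- **Clerical origin.** The fMRI period list is identical to the sleep-monitoring list in the same section and may simply have been carried over. It still does not describe the scans.

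Appendix A, the visit schedule, is not legible in the text available, so Day 21 could not be checked there. The two readable schedules agree with each other that it has no session.

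**Conclusion.** The point holds. Set A and the fMRI model cannot be run as written, set B mislabels one of four live-in lags, and Day 83 is not a scheduled visit. These conclusions rest on the protocol's own days and need no assumption.

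The open choice after a negative preliminary test is a smaller, separate matter: roughly 2 percentage points above 5% per outcome for Intervention x Session, and only under selective reporting. That size depends on assumed correlations. The documents do not support a claim that the conditional rule as such inflates error.

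The effect is confined to Objective II. Body mass is the primary endpoint and lean body mass drives the sample size, so neither is touched.

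**What to change.** Amend Objective II: Statistics before group-coded data are seen.

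1. Reconcile the session days with the Phase 2 and cognitive-testing schedules. In set A use the scheduled Day 20 session and state lags of 5, 6, 6 and 6 days. Where set B is described, label Day 15 as same-day.
2. Replace Day 83 with EOS.
3. Give the fMRI Period factor three levels, one per phase.
4. Name Intervention x Pre-post as the term that decides the branch, and state the level at which it is tested.
5. When that test is negative, commit to one analysis: the model on all scheduled sessions (Days 13, 15, 20, 22, 27, 29, 34, 36, 41, 54 and EOS).
6. In either branch, report the between-group change from Day 13 to Day 41 as the end-of-intervention contrast.

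The cost is wording only, with no new visits or data. The one drawback is that the all-sessions model mixes times since dose (live-in lags 0, 5, 1, 6, 1, 6, 1 and 6 days). Set A with Day 20 can serve as a sensitivity analysis with nearly constant lag.
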